1.0 Objectives / Specific Aims

The overall aim of this proposed effort is to test transcutaneous auricular neurostimulation (tAN) as a therapeutic for opioid withdrawal and neonatal abstinence syndrome (NAS).

We hypothesize that tAN delivered for up to 60 minutes during peak withdrawal (1h before next morphine dose) will be safe, well tolerated and will decrease Finnegan withdrawal scores and shorten the length of morphine treatment compared with historical data.

Aim 1: Determine the safety and feasibility of auricular neurostimulation therapy in neonates with opioid withdrawal or NAS.

We hypothesize that auricular neurostimulation is safe and tolerable in both a single session, and 12-day treatment course. Furthermore, we believe target engagement can be validated by measuring stimulation-induced reductions in heart rate. Milestone: No adverse events of bradycardia (HR < 80 bpm), worsening of swallowing or feeding, skin irritation, or elevation of Neonatal Infant Pain Scores.

Aim 2: Demonstrate that auricular neurostimulation therapy in opioid withdrawing or NAS neonates reduces the Finnegan and/or WAT-1 scores from pre- to post-stimulation. We have used ear electrodes for taVNS in a similar stuy (#67997). However, in this prospective, open-label study we will use a novel, non-significant risk auricular neurostimulation device and ear electrodes to study 20 opioid withdrawing or NAS neonates at the Medical University of South Carolina. We aim to show a clinically-meaningful reduction in Finnegan scores, the routine assessment that includes 21 signs of withdrawal (Finnegan 1992). Alternatively, in infants who receive both opioids and benzodiazepine analgesics, we aim to show a clinically-meaningful reduction in Withdrawal Assessment Tool (WAT-1) scores, which is a validated, 11 item/12 point scale used to monitor opioid withdrawal in pediatric patients (Franck 2008). In the study, we will deliver up to 60 minutes of tAN 1 hour prior to each morphine administration, up to 4 times per day for up to 12 days. If morphine is weaned off at or before 10 days, a weaning phase for tAN will begin on the following day for 2 days: tAN Weaning Day 1: deliver tAN twice tAN Weaning Day 2: deliver tAN once We will assess each patient with standard Finnegan scores and/or WAT-1 before and after stimulation, and monitor use of morphine throughout the study. We expect a 25% reduction in Finnegan/WAT scores from before to after sessions of auricular neurostimulation.

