2.0 Background

NAS is a condition in which infants undergo withdrawal after exposure to prescription or non-prescription opioids such as morphine, methadone or heroin in utero (Finnegan 1992). The withdrawal is characterized by hyperirritability of the central nervous system and respiratory, gastrointestinal, and autonomic symptoms (Finnegan 1992). These symptoms usually appear within 24 to 72 hours after birth. Opioid withdrawal is characterized by CNS dysfunction with loss of glutamate homeostasis, glutathione dysregulation and oxidative stress(McCLure EA e tal, 2014) leading to poor neuronal health and clinical symptoms of hyperirritability, hypertonicity, tremors, high-pitched crying, tachypnea, gastrointestinal symptoms, sweating, temperature elevation, sneezing and nasal congestion, and poor feeding, emesis, and loose stools.

From 2000 to 2012 there was a five-fold increase in the number of babies born with opioid withdrawal due to Neonatal Abstinence Syndrome (NAS, Patrick SW, et al., 2015). It is estimated that one baby is born every 25 minutes addicted to opiates (Patrick, et al. 2012). In 2012, term infants being treated for NAS stayed on average 16.9 days (compared to 2.1 days for other newborns), often in a neonatal intensive care unit (NICU). The length of stay has increased to 25 days in a neonatal intensive care unit (NICU) at an average treatment cost of \$66K (Barlow 2017, Sanlorenzo 2018). Hospital costs totaled \$1.5 billion, with 81% paid by state Medicaid programs (Patrick, et al. 2015). Despite improved recognition of NAS and early implementation of treatment (both pharmacologic and non-pharmacologic), One of the most important reasons for the difficulty in managing slow withdrawal in neonates is polydrug dependency of the mother, as opiates plus another substance of abuse has become increasingly common (Grim, 2013).

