4.0 Study Endpoints

Safety Outcomes: 1) Skin irritation, assessed by staff daily. 2) NIPS pain scores recorded during treatment.

Efficacy Outcomes: 1) Finnegan scores before and after tAN will be recorded at each session or WAT-1 scores will be recorded with hands on care . 2) Duration of morphine weaning. 3) Length of stay We will also collect data on developmental outcomes from a short motor test in the nursery and from routine clinic visits to the NICU high-risk follow-up clinic up to 24months.

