5.0 Inclusion and Exclusion Criteria/ Study Population

Inclusion criteria: Neonates or infants with opioid withdrawal or NAS who have withdrawal scores requiring morphine replacement therapy. They must be clinically stable, on minimal respiratory support (Continuous positive airway pressure (CPAP), nasal cannula, or room air), >33 weeks gestational age at enrollment, and currently receiving replacement therapy for opioid dependence.

Exclusion criteria:

- 1) Unstable infants or those requiring significant respiratory support.
- 2) Repeated episodes of autonomic instability (apnea or bradycardia) which are not self-resolving *
- 3) Infants <33weeks gestation at enrollment.
- 4) Major unrepaired congenital anomalies
- 5) Cardiomyopathy

*Preterm infants commonly have short periods of shallow or absent breathing or lower heart rate termed apnea and bradycardia, respectively, and most are being treated for these physiologic manifestations of prematurity with caffeine, an effective central stimulant. Infants are on cardiorespiratory monitors through the nursery stay with recording devices to capture events and play them back. However, nearly all of these events are self resolving, meaning the infant resolves the breathing pause or bradycardia on their own. Infants who require repeated episodes of stimulation to come out of these events are defined as *unstable*. Similarly, infants on significant respiratory support are not stable, and will not be eligible.

Stable neonates who are dependent on opioids, such as after ECMO, severe illness or brain injury, will be included in this study, as these neonates represent a population in which tAN could minimize withdrawal while not adding to burden of pharmacotherapies. Congenital syndromes may be included if the infants do not have major, unrepaired anomalies.

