6.0 Number of Subjects

Total Planned Enrollment: 20

Up to twenty neonates will be enrolled in this prospective, open-label safety and feasibility trial. The experimental paradigm consists of up to 60 minutes of tAN at the peak withdrawal time 1 hour before usual morphine dose every 3h, before feeding, up to 4 times per day, and up to 12 days or until morphine is weaned off. If morphine is weaned off at or before 10 days, a weaning phase for tAN will begin on the following day for 2 days:

- tAN Weaning Day 1: deliver tAN twice
- tAN Weaning Day 2: deliver tAN once

All consented participants will receive the active stimulation condition.

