10.0 Study Design / Methods

After obtaining consent and describing this procedure to the parents and all members of the baby's care team, we will first deliver stimulation per our protocol in #67997 to determine the perceptual threshold. We will use the identical method for determining the intensity for PT, which has proven to be safe as in our taVNS study in infant feeding. We will start with 0.2mA with a 250µs, 5Hz in vagus and 100Hz in trigeminal nerve area, and gradually increase the intensity of the TENS unit until the baby can first feel something in their ear. We will use the facial expression change, fidgety movements to determine when the infants feel the stimulation, as in the taVNS study. This intensity will be recorded as the **perceptual sensory threshold (PT)**. The procedure is detailed below.

Determination of Perceptual Threshold

- 1. Electrode clip will be placed on the left tragus in an enrolled infant at rest. Starting at 0.2mA at 5Hz in vagus and 100Hz in trigeminal nerve area, we will deliver 5 seconds of pulses, and increase by 0.1mA until the perceptual threshold is achieved by observation of the infant's facial expression, fidgety movements. This will be termed the perceptual threshold.
- 2. We will decrease the microcurrent by $\sim 0.1 \text{mA}$ below the perceptual threshold and administer this as the taVNS treatment dose 1h before the morphine dose and before the infant is feeding, every 3h, for 60 minutes, up to 4 times per day. Current will then be held constant while pulse width and frequency will be set at $250 \mu \text{s}$ and 5 Hz in vagus area and 100 Hz in trigeminal nerve area, respectively.
- 3. Finnegan scores will be rated before and immediately after the taVNS treatment, and per usual clinical protocol. WAT-1 scores will also be rated during tAN treatment per usual clinical protocol.
- 4. Physiological data will be monitored continuously as measured by the echocardiogram (ECG).
- 5. Neonatal Infant Pain Scale (NIPS) data collected at beginning and the end of treatment session. The NIPS rating scale currently in use in the nursery is included in this submission.

taVNS Protocol

These studies will be conducted in the Shawn [name] Children's Hospital's Neonatal Intensive Care Unit (NICU).

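### The Aim 1 safety milestone rests on four event types, but Section 4.0 lists only two as safety outcomes, and worsening of swallowing or feeding has no measure in the protocol

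*Protocol*

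**What the plan says.** Under Aim 1 (Section 1.0) the protocol states: "Milestone: No adverse events of bradycardia (HR < 80 bpm), worsening of swallowing or feeding, skin irritation, or elevation of Neonatal Infant Pain Scores". Section 4.0 gives the complete list of safety outcomes: "Safety Outcomes: 1) Skin irritation, assessed by staff daily. 2) NIPS pain scores recorded during treatment". Efficacy and developmental outcomes follow, and none of them is described as a measure of heart rate, swallowing or feeding.

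On heart rate, step 4 of the procedure in Section 10.0 says: "Physiological data will be monitored continuously as measured by the echocardiogram (ECG" (the abbreviation suggests that the electrocardiogram is meant). Section 5.0 adds that infants are on cardiorespiratory monitors throughout the nursery stay. The same section says of apnea and bradycardia in preterm infants that "nearly all of these events are self resolving, meaning the infant resolves the breathing pause or bradycardia on their own", and it excludes only repeated episodes that do not resolve by themselves. Section 15.0 refers to bradycardia related to stimulation and expects none.

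On feeding, Section 2.0 includes "poor feeding, emesis, and loose stools" among the clinical signs of withdrawal. In this trial's procedures feeding is only a time marker: sessions are given "before the infant is feeding, every 3h, for 60 minutes".

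On pain, step 5 in Section 10.0 has "Neonatal Infant Pain Scale (NIPS) data collected at beginning and the end of treatment session", and the Safety Monitoring text also records an initial level before the daily threshold-finding.

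Section 6.0 describes the design: "Up to twenty neonates will be enrolled in this prospective, open-label safety and feasibility trial".

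**The concern.** Safety and feasibility are what this trial says it will deliver. The Limitations text in Section 10.0 concedes that, without randomisation, the effect on morphine weaning cannot be established, and falls back on showing feasibility and safety. The milestone is the only stated criterion for safety, so it should be possible to judge it from the outcomes the protocol tells staff to record.

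For swallowing and feeding it is not. Because infants in withdrawal may already feed poorly, worsening can only mean a change from some earlier state, and no earlier state is recorded. With nothing recorded, no event can be counted, and the absence of counted events would read as success. Heart rate is a smaller gap, but a visible one: Aim 1 uses a stimulation-induced fall in heart rate as evidence of target engagement and Section 15.0 names it as a risk, yet bradycardia is not on the outcome list.

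**Working it through.** The protocol gives no safety sample size, power or event rate (Section 12.0 calls the enrolment a convenience sample), so there is no figure to reproduce. The check is a comparison of the milestone with the rest of the text.

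**Step 1. Milestone against outcomes and procedures.**

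| Milestone component | Listed in Section 4.0? | Recorded elsewhere? |
|---|---|---|
| Bradycardia (HR < 80 bpm) | No | Yes: continuous monitoring (Sections 5.0 and 10.0) |
| Worsening of swallowing or feeding | No | No measure, baseline or time point |
| Skin irritation | Yes | Yes: daily, with the ear examined before treatment (Section 10.0) |
| Elevation of NIPS | Yes | Yes: session start and end, and before threshold-finding (Section 10.0) |

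Components not listed: 4 − 2 = 2. Components with no measure: 1 of 4.

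**Step 2. Could another instrument supply the feeding measure?** Three candidates appear in the text.
- The Finnegan scale is described only as covering 21 signs of withdrawal. Its items are not set out, and it serves as an efficacy score.
- The STEP is described as a short developmental or motor test.
- The adverse-event review in Section 13.0 is general and does not define a feeding event.

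None is designated for this purpose. The remaining mentions of feeding concern the timing of sessions or the earlier taVNS feeding study.

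**Step 3. Which events count?** Infants with self-resolving bradycardia are eligible (Section 5.0), while Section 15.0 speaks of bradycardia related to stimulation. The milestone does not say which set it counts. For NIPS, the recordings listed in step 1 provide more than one possible reference value, and the milestone names none.

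**Step 4. The NIPS rule for halting or adjusting stimulation.** The Safety Monitoring text in Section 10.0 first refers to a rise of more than 3 above baseline, and in the next sentence to a score 3 above baseline.
- Rise of 2: neither wording is met.
- Rise of exactly 3: the second is met, the first is not.
- Rise of 4: both are met, if the second is read as at least 3.

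The wordings therefore differ at exactly 3.

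**Illustration only.** If every event of any type counted and the per-infant risk were p, the chance of no event in n = 20 infants would be (1 − p)^20. For assumed p of 1%, 5% and 10% this gives 0.99^20 = 0.818, 0.95^20 = 0.358 and 0.90^20 = 0.122. With 0 of 20 observed, the one-sided 95% upper bound is 1 − 0.05^(1/20) = 0.139. The protocol supplies none of these rates.

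**The case against.** The best defence is that much of this belongs in other documents. Attribution rules, the choice among recorded baselines and interval estimates are commonly left to an SAP or a case-report form. Case-report forms are mentioned in Section 15.0 but are not shown. The milestone also says adverse events of bradycardia rather than any bradycardia. Section 5.0 treats self-resolving episodes as part of prematurity, and Section 10.0 plans to relate NIPS increases to the stimulation period. Read together, these suggest that stimulation-related events are meant. No go/no-go decision or stopping rule is tied to the milestone.

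Most of this stands, and it reduces the counting rule and the NIPS reference to a one-sentence clarification. It does not answer the main point. The mismatch between Sections 1.0 and 4.0 lies inside the protocol, and an analysis plan cannot analyse feeding data that the protocol gives no instruction to collect.

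A reader might infer more than the text supports:
- **That bradycardia goes unmeasured.** It does not. It has a numeric cut-off and continuous monitoring, and is missing only from the list.
- **That the NIPS recordings contradict one another.** They are compatible. What is missing is a link from one of them to the milestone.
- **That background events make the milestone likely to fail.** The remarks on how common these episodes are concern preterm infants, no section says that they reach HR < 80 bpm, and no event rate is given. The zero-event probabilities rest wholly on assumed rates.
- **That the 13.9% bound measures the defect.** It applies to any result of 0 in 20, and listing the missing outcomes would not change it.

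**Conclusion.** The point holds and should be corrected. Two of the four milestone components are absent from the safety outcomes. One of these (HR < 80 bpm) is captured anyway. The other (worsening of swallowing or feeding) is not measured anywhere in the protocol text and could be declared met without being assessed. That is the size of the defect, and it rests on a reading of the text, not on any event rate.

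It assumes that no document outside the protocol, such as a case-report form, already defines a feeding item. If one does, Section 4.0 still needs to name it. The counting rule and the NIPS reference are secondary clarifications. The two NIPS wordings for halting or adjusting stimulation are a separate inconsistency and add nothing to the main point.

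**What to change.** 1. **Section 4.0.** Add two safety outcomes: (a) HR < 80 bpm over the treatment course, taken from the monitoring already in place and not limited to sessions, because Aim 1 covers a 12-day course; (b) worsening of swallowing or feeding, judged as change from the infant's own pre-treatment status, from routine feeding records or, if there are none, from a short case-report item. Report the number and proportion of infants with each of the four event types.
2. **Aim 1 milestone.** Add one sentence stating whether all events or only stimulation-related ones count, and which recorded NIPS value is the reference for an elevation.
3. **Section 10.0, Safety Monitoring.** The sponsor must reconcile the two wordings of the NIPS rule. No threshold is proposed here.

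The cost is small. Skin, NIPS and heart-rate data are already collected. Some chart extraction is needed for heart rate, and feeding may need one new item, since the protocol does not say whether it is charted. The safety summary becomes a short table in place of a single yes or no.

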Participants will receive tAN stimulation to their left ear via electrodes attached to the ear. The stimulation intensity we will use for tAN will be ~0.1mA less than PT or each infant. We will recalibrate the PT daily, and then deliver that current intensity for each session that day administered every 3h, starting 1h before the morphine dose. The current will be on for 5 minutes, off for 10 seconds, for up to 60 minutes total each session, up to 4 times per day, for up to 12 days or until morphine is weaned off. If morphine is weaned off at or before 10 days, a weaning phase for tAN will begin on the following day for 2 days. tAN Weaning Day 1: deliver tAN twice. tAN Weaning Day 2: deliver tAN once.

The nurses will score the NAS using the Finnegan scale before and after the treatment. The Withdrawal Assessment Tool (WAT-1) will also be used to assess infant withdrawal symptoms before and after treatment in infants receiving benzodiazepines and opioids (Franck 2008, 2013). The WAT-1 is an 11 item/12 point scale to monitor withdrawal and is routinely performed by nurses 3 times per 12 hour shift with hands on care.

Prior to beginning the study, Drs. [name] and [name] will perform an in-depth in service with the charge nurses of the neonatal nurseries, a limited pool of 10 nurses. They will also in-service the neonatal nurses at their staff meetings to introduce them to the study, the rationale, the protocol and the equipment. Most nurses are familiar with ear electrode stimulation from the taVNS-paired feeding study conducted over the past 18 months.

A short developmental test, the STEP, will be performed while the infant is stil in the nursery and at the first neonatal high-risk developmental clinic (outpatient) follow-up visit.

Safety Monitoring

Prior to determination of the daily sensory threshold of the infant by the study coordinator or research assistant, an initial pain level will be recorded using the NIPS. The nurse or other staff may decrease the current intensity or stop stimulation entirely if the infant shows signs of distress or an increase in NIPS score >3 above baseline. As opioid withdrawing infants frequently have higher NIPS, we will only halt or adjust stimulation if the NIPS is 3 greater than their baseline. The nursing staff routinely measure and record the NIPS throughout the day. We will monitor the relationship of increased NIPS scores to the up to 60 minute stimulation period daily.

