Switching from left to right ear in case of left ear difficulties

Skin redness at the site of tAN attachment to the ear is possible after treatment, but is expected to be transient. In order to prevent injury to the skin in contact with the device, each day the left ear will be first examined for redness or other medical device placement prior to attaching the tAN earpiece. If there is skin redness or any emergent medical needs at the site of attachment to the ear prior to each day's treatment, we will switch the site of stimulation to the right ear until redness or emergent medical needs on left ear are resolved.

Estimated Difficulties, Limitations and Time Frames

Estimated Difficulties: Many of the initial difficulties surrounding taVNS in humans, such as feasibility, were accomplished in the taVNS-feeding pilot trial at MUSC by [name] and [name] that were approved by IRB 1. Electrode placement: The ear electrode is easy to fit to the infant's ear and much less likely to become dislodged due to head movement than the ear electrodes used in our taVNS infant feeding study. However, we will make sure the staff feel comfortable placing the electrodes and be on call to assist with electrode placement as needed for night shift nurses. The program will be either on or off switch for nurses to activate, but will have ability to decrease stimulation current as needed.

Limitations: Finnegan scores may not show a difference acutely with tAN treatment, but may lead to faster morphine weaning. However, this is not a randomized study, and we will not be able to determine if this is significant, as it will have to be compared with historical control data already collected and analyzed in Pro # 63667. Nevertheless, we will show feasibility and safety, and gather data for a larger randomized study.

Estimated Time Frames. We plan on completing enrollment in this study over a 6-12 month period.

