12.0 Data Management

Limited demographic and personal health history data will be collected for the study. All screening data will be identified only by study number except for the consent form and a master enrollment file, which will be kept in a binder a the locked office, and password protected, respectively, per the requirements of the IRB.

All infants will be withdrawing from opioids, and will have had urine or meconium drug screens per clinical protocol. Also all fetal drug exposures will be a matter of clinical record, and not obtained for this study. We will not be doing any drug screening for this study. Study records will be kept confidential. However, as we will only have substance use information which is included in the clinical record and already known/reported to social services, we will not obtain a certificate of confidentiality.

Power Calculation: N/A. This is a convenience sample. We estimate we can enroll up to 20 patients within 12 months.

Statstical Analysis: tAN Finnegan scores obtained before and after will be compared within subjects by paired test.

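### Aim 2 promises to show that tAN lowers withdrawal scores, but an open-label, single-arm before/after comparison can only estimate the change over a session from any cause

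*Protocol*

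**What the plan says.** Protocol section 1.0 states Aim 2 as: "Demonstrate that auricular neurostimulation therapy in opioid withdrawing or NAS neonates reduces the Finnegan and/or WAT-1 scores from pre- to post-stimulation". Two further sentences under Aim 2 promise a clinically meaningful fall, one for Finnegan and one for WAT-1. The overall hypothesis in the same section says that tAN is going to lower Finnegan scores.

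The design and analysis behind this aim are:

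- Section 6.0: "Up to twenty neonates will be enrolled in this prospective, open-label safety and feasibility trial", and "All consented participants will receive the active stimulation condition".
- Section 10.0, under the taVNS protocol: "The nurses will score the NAS using the Finnegan scale before and after the treatment". Sections 6.0 and 17 both call the study open label. No sham session, unstimulated session or blinded rating is described.
- Sections 1.0 and 6.0 place the session one hour before the morphine dose and describe that time as peak withdrawal.
- Section 12.0 gives the analysis: "tAN Finnegan scores obtained before and after will be compared within subjects by paired test". No test is stated for WAT-1, and power is marked as not applicable.

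The limitations paragraph in section 10.0 says "Finnegan scores may not show a difference acutely with tAN treatment, but may lead to faster morphine weaning". It then says that, without randomisation, significance cannot be determined, "as it will have to be compared with historical control data already collected and analyzed". It ends: "Nevertheless, we will show feasibility and safety, and gather data for a larger randomized study".

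**The concern.** Aim 2 is worded as a causal and confirmatory claim. The paired test answers a different question: did scores change between the start and end of a session, for whatever reason? Candidate reasons other than tAN are settling, return from a peak, and expectation in nurses who know that the infant has just been stimulated. Nothing in the design or analysis separates these from a device effect.

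If the aim is judged as written, a significant paired test would satisfy it whether or not tAN did anything. The study is also meant to supply data for a larger randomised trial. If the session change were carried into that trial's planning as a treatment effect, any background change would be carried in with it.

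**Working it through.** **No figure to reproduce.** The protocol gives no power, significance level, baseline mean or SD. The 25% fall expected in section 1.0 therefore cannot be put in SD units. The main check is a reading; the arithmetic after it is illustrative.

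**What the test estimates.** For one infant, mean change over a session = effect of tAN + change that would have happened without tAN + change in how the nurse scores. With one active arm, only the sum is observed. The paired test asks whether the sum is zero. Aim 2 asks about the first term.

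**Whether the limitations text already covers this.** It makes two points.

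1. Acute Finnegan scores may show no difference. This warns of a null result, not of a fall with another cause.
2. Significance cannot be determined because comparison must be with historical controls. Section 1.0 uses historical data as the comparator for length of morphine treatment, whereas section 12.0 compares Finnegan scores within infant. The second point therefore refers to faster weaning.

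The missing-control problem is thus acknowledged for weaning but not for the outcome that Aim 2 sets out to demonstrate.

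**Illustration of what a background fall could do.** Assumptions, none of them from the documents: one mean change per infant, a two-sided 5% paired t-test, zero tAN effect, and a background fall of d SDs of the paired difference. Under these, t is noncentral with n − 1 degrees of freedom and noncentrality d√n.

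| Background fall d | n = 20: d√20 | n = 20: P(significant) | n = 10: d√10 | n = 10: P(significant) |
|---|---|---|---|---|
| 0.3 | 1.34 | 0.247 | 0.95 | 0.136 |
| 0.5 | 2.24 | 0.564 | 1.58 | 0.293 |
| 0.8 | 3.58 | 0.924 | 2.53 | 0.616 |

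With no background fall, the chance of a significant fall is 2.5%, half of the two-sided 5%.

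In points, with n = 20 and an assumed one-point background fall, the probability is 0.81, 0.56, 0.29 or 0.19 for an assumed SD of change of 1.5, 2, 3 or 4. The n = 10 columns stand for a smaller analysable number; enrolment is capped at twenty, and the protocol does not settle how many infants will have paired Finnegan scores.

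**Precision of the estimate proposed below.** The 95% half-width is t(0.975, n − 1)/√n. For n = 20 this is 2.093/4.472 = 0.468 SD; for n = 10 it is 2.262/3.162 = 0.715 SD.

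**The case against.** The protocol is modest almost everywhere else. Section 6.0 calls it a safety and feasibility trial, section 10.0 says it is not randomised and defers to a larger randomised study, section 12.0 calls it a convenience sample, and section 16.0 says only that scores may fall and that there may be no direct benefit. The measurable content of Aim 2 is already a before-to-after change, which the paired test does estimate. On this view the point is one verb and one missing sentence.

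Much of that stands. It limits the point to the claim and leaves the design alone. It does not remove the point, because the aim and the hypothesis are the statements against which the result will be judged, and the one caveat about missing controls is attached to a different outcome. A statistical analysis plan, if one exists, could not cure this: no analysis of these data supplies a comparator for the session change.

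A reader might infer more in three ways, none of which the documents support.

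- **A real effect could be masked because scores rise as the morphine dose approaches.** Sections 1.0 and 6.0 put peak withdrawal at one hour before the dose, when the session starts. A further rise from a peak sits badly with that wording.
- **The trial has a false-positive rate of 56%, or any such figure.** Every shift in the table is assumed; none is a property of this trial.
- **The sponsor will report a fall as proof of efficacy, or will size the next trial on it.** The protocol has no text on efficacy conclusions, and says only that data will be gathered for the randomised study.

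**Conclusion.** The point holds as one about the claim. Aim 2 and the Finnegan part of the hypothesis assert a causal effect that an open-label, single-arm, before/after comparison cannot establish, and the limitations text does not say so for the session change. The single-arm design is reasonable for safety and feasibility and need not change.

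The size of the problem is unknown, because the documents give neither the change expected without tAN nor a way to separate it. The calculations show only that it need not be small: under the stated assumptions, background falls of 0.3 to 0.8 SD would yield a significant test in about 25% to 92% of trials of 20 with no device effect. The conclusion rests on the design and the wording, not on those figures.

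**What to change.** 1. **Section 1.0.** Reword Aim 2, its two sentences promising a clinically meaningful fall, and the Finnegan part of the overall hypothesis along these lines: *Estimate, with a 95% confidence interval, the change in Finnegan or WAT-1 score from before to after a tAN session.*
2. **Section 12.0.** Report the mean paired change with its 95% confidence interval alongside the paired test, for Finnegan and, where before and after scores exist, for WAT-1. The condition is needed because the protocol describes WAT-1 timing in three ways: with hands-on care (section 4.0), during treatment (section 10.0, step 3) and before and after treatment (section 10.0, taVNS protocol).
3. **Section 10.0, Limitations.** Add: *Without a sham or unstimulated comparison and blinded scoring, the change in score over a session cannot be attributed to tAN; it will be used to plan the larger randomized study.*

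Cost: wording and one reported interval, with no extra infants, scores or visits. The downside is a more modest claim, since the study alone would not support an efficacy statement. The estimate will also be imprecise: about ±0.47 SD of the paired difference with 20 infants and ±0.72 SD with 10.
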